### 5.6.3.2. Vital Signs and Physical Examination Findings

Continuous vital sign parameters including temperature, respiratory rate, weight, pulse, blood pressure (systolic and diastolic) will be summarized at each assessment time point. Change/Percent change from baseline will be summarized for the intervention arm and analysis phase. Descriptive statistics (mean, standard deviation, median, minimum and maximum) will be presented.

Abnormality criteria (based on criteria defined below) will be applied to baseline and postbaseline values. For baseline values, increase or decrease criteria are not applied.

Postbaseline values will be considered TE if they meet both value and change criteria in the table below.

For criteria that do not include an increase or decrease from baseline:

- TE will be concluded if the postbaseline value is above the upper limit and the baseline value is below the upper limit (eg, Normal or Low). The same applies to the postbaseline value being below the lower limit with the baseline value being above the lower limit (eg, Normal or High).
- If the baseline value is missing, a postbaseline abnormality will always be considered as TE.

Incidence of vital signs during intervention, as defined in [Table 5](#), will be summarized for participants who had a baseline assessment and at least 1 postbaseline assessment for that vital sign. A listing of participants with treatment-emergent vital signs will be presented, along with a listing of all vital sign measurements.

Physical examinations including visual/audiology tests are summarized in frequency tables.

**Table 5: Clinically Important/Markedly Abnormal Vital Signs**

Vital Sign	Criteria
Pulse	>[120] bpm and with >[30] bpm increase from baseline
	<[50] bpm and with >[20] bpm decrease from baseline
Systolic blood pressure	>[180] mm Hg and with >[40] mm Hg increase from baseline
	<[90] mm Hg and with >[30] mm Hg decrease from baseline
Diastolic blood pressure	>[105] mm Hg and with >[30] mm Hg increase from baseline
	<[50] mm Hg and with >[20] mm Hg decrease from baseline
Temperature	>[38]°C and with >=[1]°C increase from baseline
Respiratory rate	>[20] breaths per minute
Weight	increase [10%] kg from baseline
	decrease [10%] kg from baseline

### 5.6.3.3. Electrocardiogram

The ECG parameters that will be analyzed are heart rate, PR interval, RR interval, QRS interval, QT interval, and corrected QT (QTc) interval using the correction method, Bazett's formula (QTcB), Fridericia's formula (QTcF).

Bazett's formula:  $QTcB \text{ (msec)} = QT \text{ (msec)} / (RR \text{ (msec)}/1000)^{1/2}$ ; if RR is missing, use  $QT \text{ (msec)} * (HR(bpm)/60)^{1/2}$

Fridericia's formula:  $QTcF \text{ (msec)} = QT \text{ (msec)} / (RR \text{ (msec)}/1000)^{1/3}$ ; if RR is missing, use  $QT \text{ (msec)} * (HR(bpm)/60)^{1/3}$ .

For the time points on which triplicate ECGs apply, a rounded mean value to the nearest integer per triplet will be calculated per time point before any further handling. This round mean value will be used through the entire analysis also in case of 1 or 2 missing values.

ECG records with partial dates (any of day/month/year is missing) will not be used in analysis except in the listings.

If heart rate (HR) is missing, it will be calculated using RR (if available) and rounded to the integer value (see the formula below) before any further handling if applicable.

$$\frac{1000}{RR(ms)} = \frac{HR(bmp)}{60}$$

HR from the vital signs section (ie, pulse) will not be used in this ECG analysis section. RR values (if applicable) will only be listed. Recalculated HR values will be flagged.

The number and percentage of participants with QTc interval will be summarized at each scheduled time point. The number and percentage of participants with QTc interval increases from baseline to the maximum postbaseline value will be summarized. Refer to the following table for summary categories.

Criteria for Abnormal QTc Values and Changes from Baseline	
QTcF/QTcB value	<=450
	>450 – 480
	>480 – 500
	>500
QTcF/ QTcB change from baseline	<=30
	>30 – <=60
	> 60

A shift table will be provided summarizing the shift from baseline to maximum QTc interval classification over time

Descriptive statistics of ECG parameters and change/percent change from baseline will be summarized at each scheduled time point.

If ECG measurements are repeated at a visit, they will be averaged. The averaged value will be considered the 'Visit' ECG result.

Abnormality criteria (based on criteria defined below) will be applied to baseline and postbaseline values.

Postbaseline abnormalities will be compared with their corresponding baseline result:

- TE will be concluded if the postbaseline value is above the upper limit and the baseline value is below the upper limit (eg, Normal or Low). The same applies to the postbaseline value being below the lower limit with the baseline value being above the lower limit (eg, Normal or High).
- If the baseline value is missing, a postbaseline abnormality will always be considered as TE.

The number and percentage of participants with treatment-emergent ECG values will be presented by intervention group in analysis phase over time:

- Heart rate (bpm): [ $<50$ ] and [ $>100$ ]
- PR interval (msec): [ $<120$ ] and [ $>200$ ]
- RR interval (seconds): [ $<0.6$ ] and [ $>1.2$ ]
- QRS interval (msec): [ $>120$ ]
- QTcF/ QTcB (msec): [ $>500$ ]

The interpretation of the ECGs as determined by a qualified physician (investigator or qualified designee) will be displayed by the number and percentage of participants meeting the normality criteria. The interpretation will be summarized over time.

Listings will be produced for all ECG data including unscheduled visit data. A listing of clinically relevant ECG abnormalities will also be provided.

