### 2.3.3. Benefit-risk Assessment for Study Participation

Based on the available data and proposed safety measures, the overall benefit/risk assessment for this study is acceptable for the following reasons:

- Only participants who meet all inclusion criteria and none of the exclusion criteria (specified in Section 5) will be allowed to participate in this study. The selection criteria include adequate provisions to minimize the risk and protect the well-being of participants in the study.
- Safety will be closely monitored throughout the study:

- In general, safety evaluations will be performed at scheduled visits during the study as indicated in the Section 1.3.
- Triplicate ECG will be assessed at scheduled visits during the study. The result of ECG will be read by not only investigators but also central ECG monitors. Independent Data Monitoring Committee (IDMC) will review the data frequently.
- A futility analysis will be implemented to evaluate early the benefit/risk balance.
- Optional cohort is planned to ensure the opportunity to receive the BDQ containing regimen for Group B participants who could not achieve sputum culture conversion at Week 24.
- Participants can switch to individualized treatment based on the result of microbiological assessment and clinical worsening at the discretion of investigators.
- Any clinically significant abnormalities (including those persisting at the end of the study/early withdrawal) will be followed by the investigator until resolution or until a clinically stable endpoint is reached.

Taking into account the measures taken to minimize risk to participants of this study, the potential risks identified in association with BDQ are justified by the anticipated benefits that may be afforded to participants with MAC-LD.

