#### **Blinding**

As this is an open-label study, blinding procedures are not applicable. However, the microbiological results from Week 2 to Week 24 will be blinded to the investigators, site staffs and participants until the completion of the other assessments at Week 24 by the investigators. In order to maintain the blind, the investigator should not perform microbiological tests for acid-fast

bacillus at the study site after Day 1 until completion of the assessments other than microbiological assessments at the Week 24 except in emergency situations related to subject safety or chemotherapy. In case the investigators need to know the microbiological result to decide if participants should be switched to an individualized treatment regimen or continue the study treatment regimen, due to clinical worsening, the investigators can access the microbiological result from the central laboratory (for the detailed procedure, refer to the Procedure for Confirmation and Reporting of Results of Blinded Sputum Culture Including Collection of Samples for Microbiology Test). Sponsor except for specific personnel listed below must keep the blinding of all the microbiological assessment after Week 2 until unblinding takes place for the primary analysis.

In addition, sponsor personnel involved in monitoring of the study sites and personnel involved in management operation of the central laboratory etc. are excluded from maintenance of blinding for microbiology assessments, taking into account that sponsor needs to confirm that investigators and etc. comply with the protocol and the decision to switch to individualized treatment regimen and the optional cohort is made based on the appropriate process. Details will be provided in the statistical analysis plan (SAP).

The interim (futility) analysis is detailed in Section [9.5, Interim Analysis](#).

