### **8.2.3. Electrocardiograms**

During the collection of ECGs, participants should be in a quiet setting without distractions (eg, television, cell phones). Participants should rest in a supine or sedentary position for at least 5 minutes before ECG collection and should refrain from talking or moving arms or legs. If blood sampling or vital sign measurement is scheduled for the same time point as ECG recording, the procedures should be performed in the following order: vital signs, ECG(s), blood draw.

At each time point at which triplicate ECGs are required, 3 individual ECG tracings should be obtained as closely as possible in succession, but no more than 2 minutes apart. The full set of triplicates should be completed within 5 minutes and must be of good quality (stable baseline, free of interference and artefact). ECGs will be recorded at a paper speed of 25 mm per second until 4 regular consecutive complexes are available. If the record is unclear due to the noise, ECGs will be repeated after 1 or 2 minutes, and the clearer recording will be adopted as an original recording. In principle, 2 original ECG recordings will be provided. One original recording will be stored at the study site and another will be sent to a central cardiologist designated by the sponsor for review. Submission of ECG to a central cardiologist will be done by transmission or send a hardcopy ECG if transmission is not possible for any reasons (refer ECG manual for details). The ECG machine dedicated for this study must be used. All tracings will be transmitted for blinded central analysis. Participants found to have a QTcF  $\geq 500$  ms or an increase from baseline (mean of triplicates on Day 1) of  $>60$  ms on ECG at any point during the treatment period will be further investigated. The ECG should be repeated and if confirmed, the investigator should attempt to identify the cause, including checking and correcting abnormal  $K^+$ ,  $Ca^{+2}$ , and  $Mg^{+2}$ . If the participant is taking any drugs suspected of causing QT prolongation, they should be withheld, and the tests repeated after sufficiently long washout to try to identify the cause. Any QTcF prolongation to  $\geq 500$  ms or an increase from baseline (mean of triplicates on Day 1) of  $>60$  ms while on study intervention is considered a notable event and should be reported immediately to the sponsor.

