## 5.6. Safety Analyses

Safety and tolerability will be evaluated throughout the study from signing of the ICF onwards until the last study-related activity (end of study/early withdrawal).

All safety analyses will be based on the safety analysis set based on actual intervention received, unless otherwise specified. All summaries will be descriptive, and no inferential methods will be used to compare intervention arms for safety.

Safety and tolerability will be assessed by evaluating treatment emergent-adverse events (TEAEs), ECGs, physical examinations, vital signs measurements, clinical laboratory tests, pregnancy testing, and management of common expected toxicities.

For all continuous safety variables, descriptive statistics by intervention group will include the N, mean, standard deviation, median, minimum, and maximum. Categorical variables will be summarized by intervention group using frequency counts and percentages.

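### The SAP's by-arm ECG normality table rests on the unmasked investigator's interpretation although all tracings go for blinded central analysis, and the SAP does not name the source of the ECG intervals

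*SAP*

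**What the plan says.** **The table.** SAP 5.6.3.3: "The interpretation of the ECGs as determined by a qualified physician (investigator or qualified designee) will be displayed", as counts and percentages of participants meeting the normality criteria, over time. SAP 5.6 summarizes categorical safety variables by intervention group, so this is a by-arm table.

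**Who is masked.** Protocol 6.3, under Blinding: "As this is an open-label study, blinding procedures are not applicable". The only exception given there is for microbiological results.

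**The central reading.** Protocol 8.2.3, and footnote v of the Schedule of Activities in the same words: "All tracings will be transmitted for blinded central analysis". Protocol 8.2.3 also provides for two original recordings. One stays at the site and "another will be sent to a central cardiologist designated by the sponsor for review". Protocol 2.3.3, justifying the benefit-risk balance: "The result of ECG will be read by not only investigators but also central ECG monitors".

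**The numeric ECG analyses.** SAP 5.6.3.3 bands QTcF and QTcB at 450, 480 and 500 ms and their changes at 30 and 60 ms: "The number and percentage of participants with QTc interval increases from baseline to the maximum postbaseline value will be summarized". It adds a shift table to the maximum QTc and limits for heart rate, PR, RR, QRS and QTc: "The number and percentage of participants with treatment-emergent ECG values will be presented by intervention group in analysis phase over time". No source is named for these values.

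**The listing.** SAP 5.6.3.3 promises a listing of clinically relevant ECG abnormalities and names no reader.

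**Status of the comparison.** SAP 5.6: "no inferential methods will be used to compare intervention arms for safety".

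**The concern.** Protocol 2.3.1 names QT prolongation with BDQ and/or clarithromycin (CAM) as a known risk. Both arms take CAM, so the contrast between arms is what isolates BDQ. Calling a tracing normal or abnormal is partly a judgement. A reader who knows the arm may over-call borderline tracings in Group A, or under-call them if used to seeing small changes on BDQ. Either way, part of a difference in the table could come from the reader and not from the drug.

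The protocol plans a masked reading of the same tracings, but the SAP gives it no role. SAP Appendix 2, which records departures from the protocol's planned analyses, mentions only the dropped per-protocol set. So the documents give no reason for leaving the central reading out.

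Waveform findings deserve particular care. Protocol 9.4.6 asks for clinically relevant waveform changes from baseline to be reported, and gives T-wave morphology and U-waves as examples. Interval cut-offs cannot capture these. Among the outputs in SAP 5.6.3.3, they could show only in the interpretation table, the listing of clinically relevant abnormalities, or the general listing of all ECG data.

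**Working it through.** **1. Which outputs depend on a reader's judgement, and whose?** All are from SAP 5.6.3.3.

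| Output | Rests on | Source the SAP names | Position |
|---|---|---|---|
| Interpretation (normality), by arm | normal/abnormal call | investigator or qualified designee | open to bias |
| QTcF/QTcB bands, change bands, shift to maximum | measured intervals, triplicate means, fixed cut-offs | none | less open to judgement; source missing |
| Treatment-emergent heart rate, PR, RR, QRS, QTc | measured values, fixed limits | none | same |
| Listing of clinically relevant abnormalities | judgement | none | cannot be classed as masked or unmasked |

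The missing source for intervals carries over to the QTcF plots and correlations against plasma concentration in SAP 5.7.2. Only the first row shows a stated rule that uses the unmasked reader.

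**2. When can the bias act?** Only on tracings read after the arm is known. Screening tracings precede randomization on Day 1, so they are not exposed.

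**3. How large could it be?** The plan has no ECG figure to reproduce. The only design figure used here is the 62 per arm from the sample size section, and only for a standard error. That figure does reproduce: 10% against 30%, two-sided 5%, no continuity correction, gives 62 per arm and 80.3% power. The ECG point does not depend on it.

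Everything else is assumed:
- the same true abnormal rate *t* in both arms, from 10% to 40%;
- every truly abnormal tracing is called abnormal;
- site-reader specificity of 95% in Group B, and 90% or 85% in Group A.

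Formulas:
- observed rate = t + (1 − t)(1 − specificity)
- false difference = (1 − t)(specificity in B − specificity in A)
- standard error = √[pA(1 − pA)/62 + pB(1 − pB)/62]

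Example with t = 20% and 90% in Group A: Group A = 0.20 + 0.80 × 0.10 = 28%; Group B = 0.20 + 0.80 × 0.05 = 24%; difference 4 points; standard error √[(0.28 × 0.72 + 0.24 × 0.76)/62] = 7.9 points.

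| True rate | Specificity in A | Observed A | Observed B | False difference (points) | Standard error (points) |
|---|---|---|---|---|---|
| 10% | 90% | 19.0% | 14.5% | 4.5 | 6.7 |
| 10% | 85% | 23.5% | 14.5% | 9.0 | 7.0 |
| 20% | 90% | 28.0% | 24.0% | 4.0 | 7.9 |
| 20% | 85% | 32.0% | 24.0% | 8.0 | 8.0 |
| 40% | 90% | 46.0% | 43.0% | 3.0 | 8.9 |
| 40% | 85% | 49.0% | 43.0% | 6.0 | 8.9 |

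With equal specificity the false difference is 0. Swapping the two specificities reverses the sign. In this range the false difference is about 0.3 standard errors (3.0/8.9) to 1.3 standard errors (9.0/7.0) at one visit. It would be hard to tell from chance at a single visit. Unlike chance, it could repeat in the same direction across visits.

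**The case against.** The strongest reply is that QT risk is not judged from this table. It is judged from averaged triplicate measurements against fixed limits, and the QT discontinuation rules in Protocol 7.1 and 8.2.3 also use numeric QTcF. Both arms take CAM and follow the same ECG schedule, so site readers have reason to look for QT effects in Group B too. Safety is descriptive, and the investigator's interpretation is a legitimate record of site judgement. Much of this stands, and it limits the point to one table. It does not remove the point: by-arm percentages are compared whether or not they are tested, and waveform findings fall outside the numeric tables.

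Stronger readings that a reader might infer, and why the documents do not support them:

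- *The whole ECG harm comparison is biased.* Only the interpretation table is tied to the unmasked reader.
- *The QTc intervals and the abnormality listing are unmasked readings.* Their source is unstated, which is a gap and not evidence of site values. A listing is also not a comparison of arms.
- *The false difference is large.* Assuming a 20% true rate, and 10% to 25% of normal tracings over-called in Group A with none in Group B, gives 0.20 + 0.80 × 0.10 = 28% to 0.20 + 0.80 × 0.25 = 40% against 20%, or 8 to 20 points. None of these inputs is in the documents, and zero over-calling in Group B is hard to defend when both arms take CAM.
- *A central normal/abnormal result is already in the database.* The protocol provides for transmission and central analysis. It does not say that an interpretation is returned or loaded.

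The term qualified designee is also undefined. A central reader is not strictly excluded, although the wording points to the site.

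**Conclusion.** The point holds for one descriptive table. As written, SAP 5.6.3.3 bases the by-arm normality display on a reader who knows the arm, while the protocol requires a blinded central analysis of all tracings that the SAP does not use. The resulting bias is avoidable, and neither its size nor its direction can be derived from the documents. The 3 to 9 points above illustrates one set of assumptions and is not an estimate.

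For the intervals and the abnormality listing, the fault is only that the source is not named. The primary endpoint, sample size and power are untouched.

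The conclusion assumes that the designee is site staff, and that the protocol's blinded central analysis means masked to treatment arm. Neither is spelled out. It is worth correcting because the table bears on a named known risk and the masked reading is already part of the protocol.

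**What to change.** In SAP 5.6.3.3:

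1. Base the by-arm normality table on the blinded central reading.
2. Name the central reading as the source of the interval values, including QTcF in SAP 5.7.2, and of the listing of clinically relevant abnormalities.
3. Keep the investigator's interpretation as a listing. A table of central-versus-local agreement by arm is optional.
4. State a fallback to the local reading for tracings with no central one, and flag those tracings.

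The cost is SAP wording and, for the normality table, a different data source. No visit, endpoint, sample size or clinical rule changes. The sponsor must first confirm that the central reader returns a normal/abnormal interpretation and that it reaches the analysis database. If it does not, the SAP should say so, label the table as an unmasked site reading, and still name the source of the intervals and the listing.

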#### **5.6.3.4. Pregnancy testing**

Additional serum or urine pregnancy tests may be performed, as determined necessary by the investigator or required by local regulation, to establish the absence of pregnancy at any time during the participation in the study. A listing of participants who pregnancy will be provided

### **5.7. Other Analyses**

#### **5.7.1. Pharmacokinetics**

PK analyses will be performed on the PK analysis set, defined as participants who have received at least 1 dose of any study intervention and have at least 1 valid blood sample drawn for PK analysis.

All plasma concentrations below quantification limit (BQL) or missing data will be labeled as such in the concentration data presentation. All subjects and samples excluded from the analysis will be clearly documented in the Clinical Study Report.

##### **5.7.1.1. Statistical Analysis of Pharmacokinetics: (Descriptive Statistics)**

Descriptive statistics (N, mean, standard deviation, %CV, median, minimum and maximum) will be calculated to summarize plasma BDQ, M2, CAM and 14-OH-CAM concentrations at each sampling time point by intervention group and study day (Day 1, Weeks 2, 8, 12, 24, and 48 [For

Week 48, BDQ and M2 only]). Subjects will be excluded from the PK analysis if their data did not allow for accurate assessment (eg, incomplete administration of the study drug; missing information of dosing and sampling times).

For descriptive statistics of the plasma BDQ, M2, CAM and 14-OH-CAM concentrations, following data handling rules will be applied:

- Data from samples outside Visit window rule and Time window rule specified in Table 2 and Table 6 will be excluded in the calculation.
- BQL will be substituted with “0 (zero)”.
- Number of plasma concentration data will be calculated based on the number of subjects with measurable value including BQL.
- When more than half (>50%) of plasma concentration are BQL at each scheduled time point, mean, median, and minimum will be shown as “BQL”, and SD, and %CV will be shown as “NC” (not-calculated), respectively. If all plasma concentrations are BQL, maximum will also be shown as “BQL”.
- When number of plasma concentration data is equal to or less than 2, only N and mean will be calculated and SD, %CV, median, minimum and maximum will be shown as “NC” regardless of the proportion of BQL, respectively.
- If the dose level is modified from the initially planned dose or prior to blood sampling day, plasma concentration data for that day will be excluded from the descriptive statistics.

